4.8 Working Definition

4.8.1 Operation time

The operation time is from the time of skin incision to the last stitch of skin closure.

4.8.2 Conversion to conventional laparoscopic cholecystectomy

Conversion to conventional laparoscopic procedure from study group will be performed where there are moderate adhesions and inflammation and difficulty to identify the important anatomy.

4.8.3 Conversion to open cholecystectomy

Conversion to open procedure from both study groups will be performed where there are difficulty to identify the important anatomy due to dense adhesions and inflammation, and complications such as bile duct injury, uncontrolled bleeding occurred.

4.8.4 Intraoperative complications

Intraoperative complications include bile duct injury, bowel injury, vascular injury and injury to nearby structures.

4.8.5 Bile duct injury

It means the injury to common bile duct with bile spillage during dissection of the Calot's triangle.

4.8.6 Bowel injury

It means the injury to gastrointestinal tract with spillage of bowel contents during procedure.

4.8.7 Vascular injury

It means the injury to cystic artery or hepatic artery with oozing or pumping blood during dissection of the Calot's triangle.

4.8.8 Injury to nearby structures

It means the injury to liver, diaphragm or omentum during procedure.

4.8.9 Postoperative complications

Postoperative complications include wound infection and prolonged ileus.

4.8.10 Postoperative outcomes

Postoperative outcomes include postoperative pain, postoperative complications and postoperative hospital stay.

4.8.11 Postoperative pain

Pain at the port insertion site, i.e., somatic pain at the abdominal wall.

4.8.12 Rescue analgesia

If VAS was more than 4 and/or if the patient suffers breakthrough pain or if the patient complains of pain between the postoperative assessment, rescue analgesia will be added with injection of intravenous tramadol 1mg/kg.

4.8.13 Wound infection

Wound infection will be described as minor if there is discharge without deep tissue destruction, and major if the discharge pus is associated with tissue breakdown, partial or total dehiscence of the deep facial layers of the wound, or if systemic illness is present.

4.8.14 Prolonged ileus

Prolonged ileus will be considered if there is no flatus passage until third postoperative day.

4.8.15 Postoperative hospital stay

Duration of hospital stay means duration from the date of operation to the date of discharge according to discharge criteria.

4.8.16 Discharge criteria

Patients will be discharged from the hospital when:

- (a) have no fever,
- (b) have no jaundice,
- (c) well tolerate to oral intake,

- (d) have recovery of bowel function,
- (e) can walk without assistance,
- (f) can manage postoperative pain with oral analgesic drugs and
- (g) no immediate postoperative complication.

4.9 List of Variables

No.	Name of variable	Operational definition	Scale of measurement
1	Age	Age in complete years	Ordinal
2	Sex	Male, Female	Nominal
3	Weight	kg	Numerical
4	Height	meter	Numerical
5	BMI	kg/m ²	Categorical
6	Operation time	Minutes	Numerical
7	Bile duct injury	Yes, No	Nominal
8	Bowel injury	Yes, No	Nominal
9	Vascular injury	Yes, No	Nominal
10	Injury to nearby structures	Yes, No	Nominal
11	Conversion to CLC from TPPOP LC	Yes, No	Nominal
12	Conversion to open from both groups	Yes, No	Nominal
13	VAS pain score	Score 0 to 10	Categorical
14	Rescue analgesia	Milligrams	Numerical
14	Wound infection	Yes, No	Nominal
15	Prolong ileus	Yes, No	Nominal
16	Postoperative hospital stay	Days	Numerical

4.10 Data analysis

Data will be recorded by using a pre-structured proforma. Data will be collected as categorical as well as numerical variables. Record files will be constructed in Microsoft Excel. The base line data will be entered into data base file. The final data file in Microsoft Excel will be exported as data base file. The categorical data will be calculated by appropriate statistical method such as Chi-square. For continuous variables, the statistical significance of patients will be analyzed by two independent Student's t test. The level of significance will be set at $P < 0.05$. After data analysis, the result will be presented in dummy tables and figures.

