4.5 Sample size determination

Target population of this study is patients with symptomatic gall stones requiring laparoscopic cholecystectomy and it will be carried out in surgical wards of No. (1) Military Hospital (700 bedded). The minimal required sample size can be calculated as follow;

$$n = \frac{(Z_{1-\alpha/2} + Z_{1-\beta})^2 (\sigma_1^2 + \sigma_2^2)}{(\mu_1 - \mu_2)^2} \quad (\text{Lwanga S.K. \& Lemeshow S., 1993})$$

n= minimum required sample size

For 95% confidence level, $Z_{1-\alpha/2} = 1.96$ (for two sided)

For power 80%, $Z_{1-\beta} = 0.84$

$\mu_1 = 2.85$ (Analgesic need after CLC) (Sreenivas et al, 2016)

$\mu_2 = 2.31$ (Analgesic need after TPPOP LC) (Sreenivas et al, 2016)

$\sigma_1 = 0.79$

$\sigma_2 = 1.02$

n = 44

After adding 10% drop out

$n_1 = 49$

The minimum required sample size will be 49 in each group, 98 in total.

By receiving the hospital statistics, patients who was treated by laparoscopic cholecystectomy were about 150 patients a year in No.(1) Military Hospital (700 bedded) Pyin Oo Lwin. So the require sample size can be met within the study period.

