4.7.9 Postoperative period

Nasogastric tube will be removed after operation. Antibiotics will be given single dose. If gallbladder perforation with bile spillage is present, antibiotics will be given total three doses.

For postoperative pain control, regular analgesic with paracetamol suppository (750 mg for <50 kg and 1 G for \geq 50 kg body weight of the patient) will be given 6 hourly up to 72 hours. The patient will be assessed the pain score by using visual analogue scale (VAS) within 12 hour, 24 hour, 36 hour and 48 hour. Rescue analgesia will be added with injection of intravenous tramadol 1mg/kg if VAS was more than 4 and/or if the patient suffers breakthrough pain or if the patient complain of pain between the assessments. Total number and dose of rescue analgesia will be recorded in the proforma.

Patient will be discharged according to discharge criteria. The postoperative hospital stay will be calculated and recorded in proforma for each patient. During the hospital stay all cases will be observed daily by the researcher for early postoperative complications till the patients are discharged from the hospital. The complications which will be observed are wound infection, prolonged ileus, bile duct injury and bowel injury. Complications will be diagnosed clinically and confirmed by relevant investigations. These complications will be recorded in the proforma. All the complicated cases will be treated under the experienced consultant surgeon together with the researcher. After resuming oral intake, oral cefixime 200 mg twice a day will be given up to 5th postoperative day. Patient will be ordered to take oral paracetamol 500 mg if they feel pain after discharge.

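### Rescue tramadol is defined in milligrams but dosed per kilogram and tested without adjustment, so body weight enters the outcome, and the protocol does not hold one scale for it

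*Protocol*

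**What the plan says.** Section 4.10 gives one rule for every continuous outcome: "For continuous variables, the statistical significance of patients will be analyzed by two independent Student's t test". It names no covariate. Section 4.9 lists rescue analgesia as numerical with milligrams as its operational definition, so that rule applies to it.

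On dosing, 4.7.9 says "Rescue analgesia will be added with injection of intravenous tramadol 1mg/kg", and 4.8.12 repeats this. Section 4.7.9 also has both the number and the dose of rescue injections recorded. The proforma (Appendix 1) has a time and a dose entry for each of up to seven injections, and it records body weight and height.

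Dummy Table 12, the only results table for this outcome, is headed in doses and carries a mean ± SD and a P value.

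Section 4.5 sizes the trial on analgesic need, 2.85 after CLC against 2.31 after TPPOP LC, with SDs 0.79 and 1.02 and no unit. It concludes: "The minimum required sample size will be 49 in each group, 98 in total".

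**The concern.** With a dose fixed per kilogram, a patient 20% heavier than another scores 20% more milligrams for the same number of injections. That part of the spread says nothing about which operation was done. Weight is already recorded, yet the stated comparison does not use it.

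Analgesic need is the quantity that sized the trial, and rescue tramadol is the closest outcome to it. At 1 mg/kg, a single injection for a 50 kg patient (the weight cut-off used for paracetamol in 4.7.9) is already 50 mg. Means of 2.85 and 2.31 are therefore not milligram totals of this drug. The trial is powered on one scale, the variable is defined on another, and the results table is worded closer to the first. In an open-label study (4.1) the scale should be fixed before results are seen. The margin is thin: about 44 evaluable patients per arm for a claimed 80% power.

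**Working it through.** **Inputs from the protocol (4.5, 4.10).** Means 2.85 and 2.31, so d = 0.54; SDs 0.79 and 1.02; two-sided 5% level; 80% power; 10% dropout; 49 per arm.

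**Assumptions, not in the protocol.** (a) The 4.5 inputs are numbers of doses, each of 1 mg/kg. (b) Body weight is independent of the number of doses. (c) The CV of body weight, c, is 0.10–0.20.

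**1. The protocol's own figure.** Sum of variances: 0.79² + 1.02² = 0.6241 + 1.0404 = 1.6645. Then n = (1.96 + 0.84)² × 1.6645 / 0.54² = 44.75. The protocol states 44 (45 if rounded up). 44/0.9 = 48.9, giving the stated 49. The figure reproduces within rounding.

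**2. Power on dose count or mg/kg.** Pooled SD = √(1.6645/2) = 0.912. Noncentrality with 44 per arm = 0.54 / (0.912 × √(2/44)) = 2.78 on 86 degrees of freedom. Power from the noncentral t is 78.4%. The normal approximation gives 79.3%.

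**3. Variance on raw milligrams.** Divide milligrams by mean weight, so the outcome is D × w, where D is the dose count (mean m, SD s) and w is relative weight (mean 1, SD c). The expected difference stays 0.54. Per arm,

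Var(Dw) = s² + c²(m² + s²).

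Summed over both arms this is 1.6645 + c² × (8.1225 + 0.6241 + 5.3361 + 1.0404) = 1.6645 + 15.1231c². Example, c = 0.20: 1.6645 + 0.6049 = 2.2694, a ratio of 1.36.

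**4. Variance after linear adjustment for weight.** Write Dw = mw + (D − m)w. Adjustment removes the first term and leaves about s²(1 + c²) per arm.

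**5. Results, 44 per arm, noncentral t.**

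| Weight CV | Variance increase, raw mg | Power, raw mg | Power, mg adjusted for weight | n per arm for 80%, raw mg |
|---|---|---|---|---|
| 0 (doses or mg/kg) | none | 78.4% | not applicable | 46 |
| 0.10 | 9% | 74.8% | 78.0% | 50 |
| 0.12 | 13% | 73.3% | 77.8% | 52 |
| 0.15 | 20% | 70.6% | 77.5% | 55 |
| 0.20 | 36% | 65.2% | 76.8% | 63 |

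Adjustment recovers most of the loss. Testing doses or mg/kg avoids it altogether.

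**6. Simulation check** (20,000 runs, gamma-distributed doses and weights, 44 per arm). Power on doses is 77%. On milligrams it is 70% at CV 0.15 and 65% at CV 0.20. With no true difference, the rejection rate on milligrams is 0.050–0.053.

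**The case against.** The strongest reply is that milligrams may never be tested. Section 4.7.9 records the number of injections, and 4.10 says that results go into the dummy tables. Table 12 is headed in doses, and its natural reading is a count. On that reading weight does not enter and no power is lost. This stands as far as it goes: analysis in milligrams is possible but not certain. It does not settle the matter, because milligrams is the only operational definition given and a heading in doses can also mean dose amounts.

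The size of the loss also depends on reading unitless inputs as dose counts and on an assumed weight CV. If weight is related to how many injections a patient needs, the variation it adds is not all irrelevant to the outcome. The protocol is silent on this.

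A reader might go further and infer any of the following, none of which the protocol supports:

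- *The unadjusted t test is wrong, or the comparison is biased.* Randomisation is in blocks without stratification factors (4.6.3), and the test holds its 5% level. A chance imbalance in weight is already reflected in the t test's standard error and is not a second problem.
- *Omitting age, sex and BMI is an error.* Naming covariates is commonly left to an analysis plan, which is not shown here.
- *Operation time is known to lose power without adjustment.* The protocol gives no target difference, SD or prognostic strength for it, so the gain may be near zero.

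**Conclusion.** The point holds for rescue analgesia. The protocol defines it in milligrams, doses it per kilogram and prescribes a test without weight, while 4.5, 4.9 and Table 12 do not share one scale. If milligrams are tested, power at 44 per arm falls from 78% to 75–65%, under the three assumptions listed above (inputs are dose counts, weight independent of dose count, weight CV 0.10–0.20). About 50–63 evaluable patients per arm would then be needed for 80% power, against 46 on doses. If dose counts are tested, nothing is lost, but the text should say so. The consequence is lost precision, with no bias and no inflated false-positive rate. The change is worth making because it costs almost nothing.

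**What to change.** - **4.5:** state the unit of 2.85 and 2.31.
- **4.9 and 4.10:** make number of rescue doses (or total mg/kg) the single rescue outcome, matching Table 12 and the sample-size inputs once their unit is confirmed. Choose one of the two, so that no second test of the same outcome is added.
- **If milligrams are kept:** compare the arms by a linear model with treatment arm and body weight, with weight named in advance.
- **In either case:** report the difference between arms with its 95% CI, and word Table 12 to match.
- **Optional:** prespecify age, sex and continuous BMI as covariates for operation time. The efficiency gain is of unknown size and may be near zero.

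The cost is about two sentences. Weight, number of injections and dose are already on the proforma, and the dosing rule is unchanged.

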4.11 Ethical Consideration

This study will be considered to be ethical because the following conditions will be fulfilled for the research.

- (i) The individual will be invited for the voluntary in the research.
- (ii) The individual is free to refuse to participate and will be free to withdraw from the researcher at any time without penalty or loss of benefits to which he or she would otherwise be entitled.
- (iii) The aim and procedure of research will be clearly explained and written informed consent will be taken before the initiation of the research work.
- (iv) The potential patient will be explained the issue understanding about the following:
 - (a) The expected duration of the individual's participation
 - (b) The individual's participation is voluntary only, not for money or other forms of materials in return for the participation.
 - (c) Both methods are the international accepted options for management of symptomatic gall stones.
 - (d) Although accepted procedure, it still has chance of complications like wound infection, pain, bleeding and injury to nearby organs, etc.
 - (e) To prevent the infection, potent broad spectrum antibiotics will be given before procedure intravenously after test dose.

- (f) Pain can be present and will be treated according to pain treatment guideline in methodology.
- (g) Complications of other will be treated accordingly.
- (h) Researcher will take the responsibility for scientific correctness in conducting research according to protocol, not allowing scientific misconduct and confidentiality for all the information and results in this study.
- (i) For the injuries or complications associated with research, the patient will be given immediate appropriate comprehensive treatment without patient's expense.
- (j) There will be no compensation for participation in the research because participation in the research is completely voluntary.
- (k) There will be no conflict of interest from any Instrument Company or Pharmaceutical Company.
- (l) The protocol will be submitted to the Institutional Ethical Review Committee to approve or clear the protocol.

5. DUMMY TABLES

Table 1. Age distribution in both study groups

No.	Age (Years)	Group A CLC		Group B TPPOP LC	
		No.	%	No.	%
1	<30				
2	31-40				
3	41-50				
4	51-60				
5	>60				
	Total				

Table 2. Sex distribution in both study groups

No.	Sex	Group A CLC		Group B TPPOP LC	
		No.	%	No.	%
1	Male				
2	Female				
	Total				

Table 3. Comparison of operation time between both study groups

Operation time (minutes)	Group A CLC		Group B TPPOP LC		P value
	No.	%	No.	%	
30 – 60					
61 – 90					
91 – 120					
>120					
Total					
Mean \pm SD					

Table 4. Comparison of intraoperative complications in both study groups

Intraoperative complications	Group A CLC		Group B TPPOP LC		P value
	No.	%	No.	%	
Bile duct injury					
Bowel injury					
Vascular injury					
Injury to nearby structures					
Others					
Total					

Table 5. Rate of conversion to open cholecystectomy in group A (CLC)

Conversion to other procedure	Group A CLC		P value
	No.	%	
Conversion to open procedure			
Total			

Table 6. Rate of conversion to other procedures in group B (TPPOP LC)

Conversion to other procedure	Group B TPPOP LC	
	No.	%
Conversion to CLC		
Conversion to open procedure		
Total		

Table 7. Comparison of rate of conversion to open procedure in both study groups

Conversion to open procedure	Group A CLC		Group B TPPOP LC		P value
	No.	%	No.	%	
Conversion to open					
Total					

Table 8. Postoperative pain assessment by VAS at 12 hour after operation

Severity of pain	Group A CLC		Group B TPPOP LC		P value
	No.	%	No.	%	
Mild					
Moderate					
Severe					
Total					

Table 9. Postoperative pain assessment by VAS at 24 hour after operation

Severity of pain	Group A CLC		Group B TPPOP LC		P value
	No.	%	No.	%	
Mild					
Moderate					
Severe					
Total					

Table 10. Postoperative pain assessment by VAS at 36 hour after operation

Severity of pain	Group A CLC		Group B TPPOP LC		P value
	No.	%	No.	%	
Mild					
Moderate					
Severe					
Total					

Table 11. Postoperative pain assessment by VAS at 48 hour after operation

Severity of pain	Group A CLC		Group B TPPOP LC		P value
	No.	%	No.	%	
Mild					
Moderate					
Severe					
Total					

Table 12. Rescue analgesic injection Tramadol requirement in both study groups

	Doses of Injection Tramadol requirement		P value
	Group A CLC	Group B TPPOP LC	
12 hour			
12 – 24 hour			
24 – 36 hour			
36 – 48 hour			
Total			
Mean \pm SD			

Table 13. Comparison of postoperative complications in both study groups

Postoperative complications	Group A CLC		Group B TPPOP LC		P value
	No.	%	No.	%	
Wound infection					
Prolonged ileus					
Others					
Total					

Table 14. Comparison of duration of postoperative hospital stays in both study groups

Duration of postoperative hospital stay (days)	Group A CLC		Group B TPPOP LC		P value
	No.	%	No.	%	
≤3					
4- 7					
8-14					
>14					
Total					
Mean ± SD					

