1.3 Justification

Cholecystectomy is one of the most common elective operations in No.(1) Military Hospital (700 bedded) Pyin Oo Lwin. In 2018, 145 cholecystectomies were done (1/700 MH OT-Registry, 2018). Almost all cholecystectomies were done by conventional laparoscopic technique. Laparoscopic cholecystectomy has rapidly replaced open cholecystectomy as a standard treatment of symptomatic gall stones.

Conventional laparoscopic cholecystectomy is still gold standard procedure, but it still has chance of complications like wound infection, pain, bleeding and injury to nearby structures such as bile duct, bowel or liver. Among these injuries, bile duct injury is common and the percentage is 1% to 2%. The rate of open conversion from CLC is less than 1% (Sreenivas et al, 2016).

Two ports plus one puncture laparoscopic cholecystectomy is also acceptable procedure but it can carry longer operation. The percentage of bile duct injury is 1% to 3%. The conversion rate to conventional procedure is about 5.45% and to open procedure is about 0.18% (Sreenivas et al, 2016). Recent studies demonstrated two ports laparoscopic cholecystectomy using 2.3 mm alligator grasper has acceptable outcome. The main advantages of this two ports LC can be performed safely, principle as the previous conventional technique, reduce number of port, less painful, better for specimen delivery, higher cosmesis with shorter hospital stay (Nasir et al, 2018). Two ports laparoscopic cholecystectomy using conventional umbilical and epigastric ports assisted by 2.3mm alligator grasper may be the method of choice when considering laparoscopic cholecystectomy on a day-case basis due to early recovery.

Therefore, the key question about two ports plus one puncture laparoscopic cholecystectomy (TPPOP LC) is whether it provides a significant advantage over conventional laparoscopic cholecystectomy technique (CLC) now in use. There is no such comparative study in Military Hospitals and Myanmar yet.

So this study will compare the outcomes between conventional laparoscopic cholecystectomy (CLC) and two ports plus one puncture laparoscopic cholecystectomy (TPPOP LC). It may also help to find out safe and effective treatment options for symptomatic gallstones patients.

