3.2 Objectives

1. To compare the operation time between conventional laparoscopic cholecystectomy (CLC) and two ports plus one puncture laparoscopic cholecystectomy (TPPOP LC)
2. To compare the intraoperative complications of both study groups.
3. To compare the conversion rate of both study groups.
4. To compare the postoperative complications, postoperative pain, postoperative hospital stay of both study groups.

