3.3 Hypothesis

Two ports plus one puncture laparoscopic cholecystectomy (TPPOP LC) is as safe and effective as conventional laparoscopic cholecystectomy (CLC).

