4.7.6 Conversion to conventional laparoscopic cholecystectomy

Conversion to conventional laparoscopic procedure from TPPOP LC group will be performed where there are moderate adhesions and inflammation and difficulty to identify the important anatomy.

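### Objective 3 compares conversion between the arms, but the only between-arm table counts conversion to open surgery and leaves out conversion to CLC, where about 97% of expected TPPOP LC conversions lie

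*Protocol*

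**What the plan says.** Section 3.2, third objective: "To compare the conversion rate of both study groups". The type of conversion is not restricted. Section 3.3 gives the hypothesis that TPPOP LC "is as safe and effective as conventional laparoscopic cholecystectomy (CLC").

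The protocol defines two conversion events. Section 4.7.6 (repeated in 4.8.2) describes the first: "Conversion to conventional laparoscopic procedure from TPPOP LC group will be performed where there are moderate adhesions and inflammation", together with difficulty in identifying the anatomy. Sections 4.7.7 and 4.8.3 describe the second, conversion to open surgery, which applies to both arms. Section 4.9 lists both as yes/no variables, "Conversion to CLC from TPPOP LC" and "Conversion to open from both groups", and the proforma in Appendix 1 has fields for both.

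Section 5 has three conversion tables:

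- Table 5: Group A only, conversion to open. It has a P value column but only one arm, so it is not a comparison.
- Table 6: Group B only, with rows for conversion to CLC, conversion to open, and a total. It has no P value.
- "Table 7. Comparison of rate of conversion to open procedure in both study groups": both arms with a P value, for open conversion alone.

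Section 4.10 says that results will be presented in the dummy tables.

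Section 1.3 gives the expected rates. For TPPOP LC: "The conversion rate to conventional procedure is about 5.45% and to open procedure is about 0.18" per cent. For CLC: "The rate of open conversion from CLC is less than 1" per cent. Section 1.2 separately says that 2–5% of laparoscopic cholecystectomies in general are converted to laparotomy.

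**The concern.** The objective covers conversion as a whole, while the planned comparison covers only one of the two kinds that the protocol defines. By the protocol's own rates, the kind left out makes up nearly all of the TPPOP LC conversions.

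The direction of the result is at stake. A surgeon deciding whether to take up TPPOP LC needs to know how often the operation is finished as planned. Table 7 can show the arms level, or TPPOP LC ahead, while the technique is abandoned more often than CLC is. Read against a hypothesis that the new technique is as safe and effective, that table could be taken as support which the full conversion count would not give.

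**Working it through.** **Inputs.** Section 1.3: TPPOP LC to CLC 5.45%, TPPOP LC to open 0.18%, CLC to open under 1%. Section 1.2: laparoscopic to laparotomy in general, 2–5%. Section 4.5: 49 per group.

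**The plan's sample size.** (1.96 + 0.84)² × (0.79² + 1.02²) / (2.85 − 2.31)² = 7.84 × 1.6645 / 0.2916 = 44.75. The plan states 44, and 44 / 0.9 = 48.9, giving its 49. Rounding up first would give 45 and then 50, which makes no practical difference here. The size was set on analgesic need; no power is stated for conversion.

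**Share of TPPOP LC conversions outside Table 7.**
- If the two rates are separate: 5.45 / (5.45 + 0.18) = 5.45 / 5.63 = 96.8%.
- If the 0.18% lies within the 5.45%: (5.45 − 0.18) / 5.45 = 5.27 / 5.45 = 96.7%.

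**Expected events at 49 per arm.**
- TPPOP LC to CLC (omitted from Table 7): 49 × 0.0545 = 2.67, or 49 × 0.0527 = 2.58 if the rates overlap.
- TPPOP LC to open (in Table 7): 49 × 0.0018 = 0.09.
- CLC to open (in Table 7): under 49 × 0.01 = 0.49 by section 1.3; 49 × 0.02 = 0.98 to 49 × 0.05 = 2.45 by section 1.2.

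**What Table 7 would probably contain.** The chance of no open conversion in Group B is 0.9982⁴⁹ = 0.92. With CLC at 1%, the chance of none in either arm is 0.9982⁴⁹ × 0.99⁴⁹ = 0.916 × 0.611 = 0.56. In that case there is nothing to test.

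**Difference between arms, TPPOP LC minus CLC, in percentage points.**

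| CLC rate used | Open only (Table 7) | Any conversion, TPPOP LC 5.45–5.63% |
|---|---|---|
| 1% (upper limit, section 1.3) | 0.18 − 1 = −0.82 | 4.45 to 4.63 |
| 2% (section 1.2, low) | 0.18 − 2 = −1.82 | 3.45 to 3.63 |
| 5% (section 1.2, high) | 0.18 − 5 = −4.82 | 0.45 to 0.63 |

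At each of these rates the two columns have opposite signs. A CLC rate below 1% widens the any-conversion gap and shrinks the open-only one. Below 0.18% the open-only sign would change too, although at 49 per arm the observed counts would most likely be zero in both arms.

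**Power for any conversion at 49 per arm** (5.63% in TPPOP LC, two-sided 0.05). With CLC between 1% and 0%, the normal approximation gives about 25% to 39%, but Fisher's exact test gives only about 4% to 6%. With 2–5% in CLC, the exact power falls to about 2% and then below 1%. By the normal approximation, 80% power would need about 234 per arm (CLC at 1%) or 135 per arm (CLC at 0%).

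An example shows why. Three conversions against none gives a two-sided Fisher P of 2 × C(49,3) / C(98,3) = 2 × 18,424 / 152,096 = 0.24. Five against none gives 0.056. Only six against none reaches significance (0.027).

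**The case against.** The strongest defence is that open conversion is the only like-for-like event. A CLC patient cannot convert to CLC, and adding ports is a lesser event than laparotomy, so pooling the two gives them equal weight. This stands as a reason to keep the open row in Table 7. It does not answer the objective, because failure to complete the assigned technique is defined in both arms and is what a comparison of conversion rates, left unqualified, asks about.

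A second defence is that conversion to CLC is not concealed. Table 6 reports it with a total, and a careful reader can set that total beside Table 5. That is true. A reader might infer that the plan hides these events, and the documents do not support this; what is missing is the comparison.

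Third, the added test would settle little at this sample size. That is also true, so the fix rests on the estimate and its interval rather than the P value.

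Three further inferences go too far:

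- That difficult TPPOP LC cases go to CLC first and so seldom reach open surgery. Sections 4.7.6 and 4.7.7 grade the triggers by severity, and direct conversion to open is provided for in both arms.
- That the any-conversion gap is at least 4.6 points. This uses section 1.3 alone and assumes that its two TPPOP LC rates do not overlap. Section 1.2 supports a much smaller gap.
- That converted patients will be moved out of Group B or dropped. Nothing in the protocol says so; the proforma and Table 6 record them under Group B. The analysis set is commonly left to an SAP, which is not at hand.

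**Conclusion.** The point holds as a mismatch between an objective and the table meant to answer it. Objective 3 is broader than Table 7, and on the protocol's own rates about 97% of TPPOP LC conversions fall outside the only between-arm comparison. That share hardly depends on whether the two rates in section 1.3 overlap.

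The size of the difference between arms is less certain. Any conversion would be about 5.5–5.6% for TPPOP LC. The gap from CLC is about 4.5 points or more with section 1.3's rate, or about 0.5–3.6 points with section 1.2's general rate, which is not specific to the four-port technique. It runs against TPPOP LC at all of these rates, while the open-only comparison would tend to look equal or to favour TPPOP LC. On section 1.3 alone the second half is a tendency and not a certainty, because its CLC figure is only an upper limit.

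A reader might infer that Table 7 is wrong and should be replaced. The documents do not support that: its content is a legitimate comparison, but incomplete for the objective it serves. The change should be made, and it is small.

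**What to change.** Keep the open-conversion row in Table 7. Add a row for any conversion from the assigned technique: TPPOP LC to CLC or to open, against CLC to open, counting each patient once. Report the difference in proportions with an exact 95% confidence interval and Fisher's exact test.

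Add one sentence to section 4.10: the trial has very low power for conversion at 49 per arm, the estimate and its interval carry the information, and a non-significant P value is not evidence of equivalence.

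The cost is one table row and one sentence. Both conversion fields are already on the proforma, so no new data are needed, and no rule about when to convert changes. The downside for the investigators is a less favourable conversion figure for TPPOP LC.

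### VAS pain is tested in four separate tables at 5% each, with no time point or summary named as the pain result and no analysis that uses a patient's four readings together

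*Protocol*

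**What the plan says.** Protocol section 4.7.9 sets four readings per patient: "The patient will be assessed the pain score by using visual analogue scale (VAS) within 12 hour, 24 hour, 36 hour and 48 hour". Objective 4 in section 3.2 is "To compare the postoperative complications, postoperative pain, postoperative hospital stay of both study groups"; it names neither a time point nor a summary for pain.

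Section 4.10 says "The categorical data will be calculated by appropriate statistical method such as Chi-square", gives the two-sample t test for continuous variables, sets P < 0.05, and sends the results to the dummy tables. The four pain tables run from "Table 8. Postoperative pain assessment by VAS at 12 hour after operation" to "Table 11. Postoperative pain assessment by VAS at 48 hour after operation". Each has mild, moderate and severe rows and its own P value column.

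No table, test or rule uses a patient's four VAS readings together. Table 12, by contrast, has total and mean ± SD rows for tramadol over the same four intervals.

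**The concern.** One objective on pain receives four P values, and no rule says how to read them. If one or two fall below 0.05, the report can claim a pain difference or deny one, and the choice would be made after seeing the data. Repeated testing at 5% also raises the chance that a chance finding at one time is reported as a pain benefit of the new technique. In addition, four readings of the same patient carry more information about an overall difference than any one of them, and the layout makes no use of this.

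**Working it through.** **Inputs from the protocol.** Four readings (4.7.9); two-sided 5% level and 80% power, and 44 per group before and 49 after a 10% dropout allowance (4.5); P < 0.05 with no adjustment stated (4.10).

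**Assumptions, not in the protocol.** Equal correlation ρ between any two readings of a patient, taken as 0.3 to 0.9, and an illustrative difference of 0.5 SD.

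**1. The plan's own figure.** (1.96 + 0.84)² × (0.79² + 1.02²) / (2.85 − 2.31)² = 7.84 × 1.6645 / 0.2916 = 44.75. The plan states 44, and 44 / 0.9 = 48.9, hence 49. The inputs are for analgesic need, so this calculation says nothing about VAS. It only supplies the group sizes used below.

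**2. False positives.** Four independent tests give 1 − 0.95⁴ = 18.5%. Correlated readings give less; the values in the table come from simulating four equally correlated normal test statistics.

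**3. Disagreement.** With a true 0.5 SD difference at all four times and 44 per arm, each test statistic has mean 0.5 × √(44/2) = 2.35. The table gives the simulated share of trials in which some but not all four tests are significant. At 49 per arm the shares are slightly lower (62%, 52% and 40% for ρ = 0.3, 0.5 and 0.7).

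**4. Precision of a joint analysis.** The mean of four readings has variance (1 + 3ρ)/4 relative to one reading. Power is that of a two-sample t test with 86 degrees of freedom and noncentrality 2.35 / √((1 + 3ρ)/4). One time point alone has 64%.

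| ρ | Variance factor | At least one significant, no true difference | Four verdicts disagree, constant 0.5 SD | Power of the average, constant 0.5 SD |
|---|---|---|---|---|
| 0.3 | 0.475 | 17.3% | about 66% | 92% |
| 0.5 | 0.625 | 15.7% | about 55% | 83% |
| 0.7 | 0.775 | 13.1% | about 43% | 75% |
| 0.9 | 0.925 | 9.3% | about 24% | 67% |

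**5. The tables as planned.** Steps 2 to 4 treat VAS as numeric. A simulation of four three-category chi-square tables (assumed control split 60/30/10% mild/moderate/severe, 44 per arm, underlying ρ 0.3 to 0.7, 1,500 runs per setting) gave about 35% power per table for a 0.5 SD shift. Verdicts were mixed in 57–72% of trials. With no difference, at least one table was significant in 17–19%. Part of that low power comes from grouping the score, which is a separate matter.

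**6. A fading effect.** Suppose the difference is 0.5, 0.375, 0.25 and 0.125 SD at the four times. The average is 0.3125 SD. At 49 per arm its power is 60%, 49% or 41% for ρ = 0.3, 0.5 or 0.7. The 12-hour contrast alone (0.5 SD) has 69%.

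**The case against.** *Tables by time are a usual way to show the course of pain, and results may truly differ over time.* As description, yes. Here, however, they are the only planned inference on VAS, each with a P value and none designated.

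*Section 4.10 says "such as" before naming chi-square, and an unseen SAP could add a model.* The wording is not exclusive. But the protocol itself fixes the table shells, the P value columns and the threshold, so this is a choice made rather than a detail left open.

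*Analgesic need, which sized the trial, is already totalled over time in Table 12.* True, and it limits the weight of the point. It does not settle the VAS comparison.

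Four stronger readings are tempting, and the document does not support them.

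- **That four tests are less able to find something.** With a constant 0.5 SD effect and 44 per arm, at least one of four t-type tests is significant in 94%, 90% or 85% of trials (ρ = 0.3, 0.5, 0.7), more than the average's 92%, 83% or 75%. The price is the raised false-positive rate and the mixed verdicts.
- **That averaging always gains.** Step 6 shows that it can lose. The protocol gives no reason to expect a constant effect, and rescue tramadol, triggered by the VAS itself, may draw later readings together.
- **That patients will lack readings.** No section says so. Regular paracetamol suppositories run to 72 hours, which suggests that most patients are still in hospital at 48 hours.
- **That the sample size is wrong for this reason.** It rests on analgesic need.

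**Conclusion.** The point holds as a defect in how the pain comparison is specified: four unadjusted tests, no designated result, and no joint use of the readings. The false-positive chance across the four is about 13–17% for ρ between 0.7 and 0.3, and about 9% at ρ = 0.9. Under a constant 0.5 SD effect the verdicts disagree in roughly 40–66% of trials for ρ between 0.7 and 0.3.

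The precision gain is conditional. It needs a roughly constant effect and a numeric score, and it shrinks from 28 percentage points of power at ρ = 0.3 (64% to 92%) to 3 at ρ = 0.9 (64% to 67%). The protocol gives neither the correlation nor the shape of the effect over time. This is a worthwhile correction to one stated objective and does not threaten the trial as a whole.

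**What to change.** Pre-specify one repeated-measures comparison of the measured 0–10 VAS: a linear mixed model with arm, time and arm-by-time as fixed effects and patient as the repeated unit. Name in advance the single contrast that is the pain result, for example the 12–48 hour average, and report it with its 95% CI. If the investigators expect the difference mainly early, they should weigh that before choosing the average, because the choice cannot be made after seeing the data. State how readings taken after rescue tramadol enter the analysis. Keep Tables 8–11 as description without P values.

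The cost is an amended section 4.10, one model in standard software, and a change to the proforma. Appendix 4 has the clinician measure the line, but part F of the proforma, as far as its text can be read, offers only mild, moderate or severe. A numeric entry is therefore needed at each of the four times before data collection. No extra patients, visits or measurements are required.
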